[Part 2 of 3 of the document. The other parts are not shown.]

- CGM glucose every 5 minutes from the Dexcom G4 Platinum CGM
- All BG measurements taken
- Insulin total dose by the BP and the patient's own insulin pump
- Glucagon total dose
- Timing and content of the meal eaten and carbohydrate amount
- Timing of meal announcement and size of meal announced
- Timing and glucose values at calibrations
- Timing and amount of carbohydrates taken for hypoglycemia
- Data from a questionnaire about attitudes and expectations regarding the BP before and after each treatment arm (see [Appendix C](#))
- Time patients were not under BP control for any reason
- List of technical faults associated with the BP including cause and resolution
- ZP4207/glucagon sampling will be collected at least hourly. If BG is <150 mg/dL, more frequent samples for plasma ZP4207/glucagon may be drawn at the discretion of the Investigator.
- Plasma glucose sampling will be collected at least hourly in parallel with ZP4207/glucagon exposure sampling. If BG is <150 mg/dL, then sampling will be every 30 minutes. If BG is <100 mg/dL, then sampling will be every 20 minutes. If BG is <80 mg/dL, then sampling will be every 10 minutes.
- Nausea and infusion site pain on a VAS at visit start (after insertion and before any drug administration), hourly, and at visit end
- Infusion site reaction according to the Draize scale at visit start (after insertion and before any drug administration), hourly, and at visit end
- Patient reports of symptoms, any other complaints, and AEs
- Vital signs including body temperature and blood pressure (at visit start and visit end) and weight
- Concomitant medications

Clinical Trial Protocol
ZP4207-16051

Version number: 6.0
Amendment 5.0
Date: 09 September 2016

- Chemistry and hematology samples (see [Appendix B](#)) at visit start and visit end
- ADA (Visit 3 only)
- 12-lead ECG at visit start and visit end
- Urine HCG pregnancy test for women of childbearing potential

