9. Vital signs including body temperature and blood pressure will be obtained at visit start and visit end.
10. At visit start and visit end.
11. Urine HCG pregnancy test only for women of childbearing potential. The date of the last menstrual period in female patients will be obtained at Visit 1 only.
12. Test for FSH level only for postmenopausal women amenorrheic for less than 1 year.
13. If indicated by history.
14. Patients will be trained in the insertion and calibration of the Dexcom G4 sensor, diabetes management (e.g., basal insulin rate adjustment by insulin pump) during fasting prior to and between the treatment visits, and trial policies and procedures.
15. Collected at least hourly. If BG is <150 mg/dL, then sampling will be every 30 minutes. If BG is <100 mg/dL, then sampling will be every 20 minutes. If BG is <80 mg/dL, then sampling will be every 10 minutes.
16. Collected at least hourly. If BG is <150 mg/dL, more frequent samples for plasma ZP4207/glucagon may be drawn at the discretion of the Investigator.
17. Once the infusion sites have been placed but no drug has yet been administered.
18. Between approximately Hour 3 and Hour 4.
19. Between approximately Hour 6 and Hour 7.
20. Before the start of dosing.
ADA = anti-drug antibodies; BG = blood glucose; BP = bionic pancreas; CGM = continuous glucose monitor; ECG = electrocardiogram; FSH = follicle-stimulating hormone; HbA1c = hemoglobin A1c; HCG = human chorionic gonadotropin; VAS = visual analog scale.

Clinical Trial Protocol
ZP4207-16051

Version number: 6.0
Amendment 5.0
Date: 09 September 2016

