Treatment with ZP4207 and marketed glucagon can result in undesired effects or complaints. Undesired effects and complaints such as gastrointestinal side effects including nausea, vomiting, and diarrhea are known side effects of glucagon administration at higher dose levels. The frequency of nausea associated with the administration of 1 mg of glucagon according to the Summary of Product Characteristics (SPC) for Glucagon is described to be between 1/10 and 1/100. The frequency of vomiting is described to be between 1/100 and 1/1000 (Novo Nordisk, 2015). Similar gastrointestinal side effects have also been observed to a limited degree in the 2 clinical trials conducted with ZP4207, again at higher dose levels. The individual doses of ZP4207 and Lilly glucagon delivered by the BP are expected to be significantly lower than doses typically associated with nausea. Episodes of low blood pressure have also been observed after administration of higher doses of glucagon and ZP4207. As with every novel drug substance, new and yet unknown side effects may also occur.

There are limited data available to describe the immunogenic potential of glucagon products available on the market, but the data available indicate that marketed glucagon only has a small immunogenic potential. A Phase 1 trial performed with recombinant human glucagon and animal derived glucagon in 75 healthy patients did not show signs of ADA measured 13 weeks after trial product administration (Eli Lilly, 2005). In the ZP4207 FHD trial, ZP4207-14013, no confirmed anti-ZP4207 or anti-glucagon antibodies were detected in any of the samples. In addition, the 5 sequential administrations of ZP4207, as applied in trial ZP4207-15007, were not associated with the development of antibodies against ZP4207 in the 18 subjects enrolled to receive ZP4207. The optimized formulation of ZP4207, as applied in the present trial is not expected to change the immunogenic potential of the Investigational Medicinal Product (IMP).

In relation to diabetes therapy, development of insulin-antibodies is documented more substantially and route of administration has been shown to influence immunogenic potential of insulins. However, these antibodies against insulin generally do not have an impact on insulin action and are thus not clinically relevant.

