6.4 Doses

The iLet and the iPhone-based BP can administer isolated insulin-glucagon doses once every 5 minutes. A single automated bolus of insulin will not exceed 3 units per 5-minute dose (30 μ l of U-100 insulin) in both systems, and a single meal-priming dose, in response to a meal announcement made by the user, will not exceed 12 units (120 μ l of U-100 insulin). A single bolus of glucagon will not exceed 80 μ g (80 μ l of 1 mg/mL Lilly glucagon or 1 mg/mL ZP4207). In prior studies, typical doses of glucagon were in the range of 2.5–40 μ g per dose. The iLet and the iPhone-based BP are capable of administering as little as ~0.5 μ l (0.05 units of U-100 insulin or 0.5 μ g of 1 mg/mL ZP4207).

It is expected that the mean total daily doses of glucagon/ZP4207 will be <1.0 mg daily as in previous studies. The mean daily glucagon dose in a previous 11-day outpatient trial was 0.5 mg/day (range 0.2–0.9 mg/day). Currently, single doses of up to 2 mg ZP4207 have been administered in clinical trials. The recommended dose of marketed glucagon for adult patients suffering from severe hypoglycemia is 1 mg as a single injection. Mean glucagon levels in previous inpatient studies have been above the normal fasting range for glucagon only 1% of the time. Therefore, the glucagon exposure of patients is expected to be modest.

6.5 iPhone-based Bionic Pancreas

Infusion Set: Patients will wear 2 FDA-approved commercially available infusion sets, 1 for insulin infusion and 1 for glucagon infusion. Infusion sets that are compatible with the Tandem t:slim infusion pump (luer lock connection) will be provided.

Continuous Glucose Monitors: One transcutaneous glucose sensor for the Dexcom G4 Platinum (Garcia, 2013) will be inserted in the abdominal SC tissue and will provide input to the controller. The sensor is powered by the battery within the transmitter that clips to the sensor and the whole assembly is held to the skin with an adhesive patch and communicates wirelessly with the BP. If the G4 sensor fails for any reason during the trial (loss of CGM signal), it will be replaced promptly.

Bionic Pancreas Control Unit: The control unit consists of a stock iPhone 4S and a Dexcom G4 Platinum receiver connected with a custom hardware interface and placed back-to-back in a custom enclosure. The G4 receiver converts the raw wireless signal from the transmitter into an estimated BG signal that is sent via a hardwired connection to the iPhone.

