7.4.1 Visit Procedures

- Patients will be asked to arrive at the visit at least 1 hour in advance of the start of the BP having fasted since 12:00 AM the night before (treatment with simple carbohydrate of up to 30 g for a low is allowed). If the patient is not fasted, the visit will be rescheduled within the visit window. If BG is >250 mg/dL, the visit will be rescheduled within the visit window. If BG is <50 mg/dL, treatment with simple carbohydrate is allowed. If the patient experiences persistent hypoglycemia, the visit will be rescheduled within the visit window. If the visit needs to be rescheduled due to hypoglycemia or hyperglycemia, trial staff will assist the patient with insulin or medication adjustments to address glycemic control. The patient will be instructed to contact trial staff later in the day if his or her BG remains uncontrolled.
- Upon arrival to the visit, the patient's weight and vital signs including body temperature and blood pressure will be documented.
- Patient reports of symptoms, any other complaints, and AEs will be reviewed.
- Concomitant medications will be recorded.
- Chemistry and hematology samples will be collected at visit start (see [Appendix B](#)).
- ADA samples will be collected before the start of dosing (Visit 3 only).
- A 12-lead ECG will be performed.
- A urine HCG pregnancy test will be performed in female patients of childbearing potential. If the test is positive, the patient will be informed of the result and the visit will be ended.

Clinical Trial Protocol
ZP4207-16051

Version number: 5.0
Amendment 4.0
Date: 02 September 2016

- Patients will complete a baseline survey about their attitudes and experience with their usual diabetes care.
- An IV catheter will be placed for blood sampling.
- Trial staff will assist the patient to calibrate their CGM, review the trial procedures again and assist with the setup of the BP system, including inserting and priming infusion sets.
- The control algorithm will be initialized only with the patient's weight. Diagnostics will be performed to ensure that the CGM device is appropriately calibrated and that all of the components of the BP systems are in working order.
- The basal rate of the patient's own insulin infusion pump will be changed to be 2-fold higher than weighted mean of the basal rate during the trial period. This is intended to increase the usage of glucagon during the treatment visit.

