- Patients will be asked to rate any nausea and/or infusion site pain on 10 cm visual analog scales (VAS) at the beginning of the visit once the infusion sites have been placed but no drug has yet been administered, then approximately at the top of every hour during the visit, and at the end of the visit. Trial staff will also evaluate their infusion sites to document any erythema or edema at the same times. If moderate or severe pain is reported or swelling or redness occurs at the infusion site, the infusion site will be replaced in a different location. If moderate or severe pain, swelling, or redness continues at the old site for more than 30 minutes after the infusion site is removed, or if moderate or severe pain, swelling, or redness occurs at the new site, all infusion sites will be removed and the patient will be discontinued from the study. Any such symptoms will be followed until resolution.
- From the start of closed loop control until approximately Hour 3, the patients will continue to fast.

Clinical Trial Protocol
ZP4207-16051

Version number: 5.0
Amendment 4.0
Date: 02 September 2016

- Between approximately Hour 3 and Hour 4, patients will be provided with a lunch meal of their choice in the Diabetes Research Center from a menu of choices from nearby restaurants. They will be asked to choose a meal that is a “typical meal” for them. The content of their meal will not be restricted in any way, with the exception that the number of carbohydrates should be in the “typical” range for them at lunch, and that they must eat the same meal at the same time during both visits.
- At approximately 15 minutes before the meal, patients will administer a bolus for the meal with their own insulin pump based on the carbohydrate count for the meal.
- After lunch is completed, the patients will not be allowed any carbohydrate intake (non-caloric drinks will be permitted) until the trial is completed (except as necessary to treat hypoglycemia), to allow the BP to control the post-prandial BG without further interruption.
- Between approximately Hour 6 and Hour 7, the patients will start a period of structured exercise.
- At the start of the exercise period, patients will restore their normal basal insulin profile so that they will not have elevated insulin levels at the end of the study period when they are to transition back to their usual care.

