- Patients will exercise on a stationary bike with a heart rate from 120-140 beats per minute for a total of 4,000 heart beats (approximately 30 minutes). Patients will rate their exercise intensity using the Borg scale every 5 minutes, with the target intensity level between 12 and 14. Heart rate will be measured every 5 minutes.
- BG measurements will be obtained off of the IV line every 10 minutes. If BG is <80 mg/dL, BG measurements will be obtained off of the IV line every 5 minutes.
 - Carbohydrates will be given for any BG <50 mg/dL according to the following protocol: Dextrose (g) = BSA (m²)/[1.7 m² (women) or 1.9 m² (men)] *15 g.
 - Repeat treatments will be given at 15-minute intervals as long as BG remains <50 mg/dL.
- If there is an interruption in the Dexcom CGM output, trial staff will assist the patient in recovering CGM data streaming. If this requires replacement of the CGM sensor, BGs will be checked every 10 minutes (every 5 minutes if BG is <80 mg/dL) using blood from the IV until the CGM is able to be calibrated again. These BGs will be entered into the BP, which will treat them as CGM values and dose insulin and/or glucagon appropriately.
- If there is a complete failure of the BP operation, patients will take over their own BG control using their personal insulin pump until the BP can be brought back online. If BP control cannot be promptly resumed (e.g., within 30 minutes), the patient may be asked to repeat that trial day once.
- Patients may choose to withdraw from the trial at any time. If they withdraw from the trial, they should alert a provider immediately.
- Just prior to the end of the study visit, vital signs including body temperature and blood pressure will be obtained and a 12-lead ECG will be performed.
- After approximately Hour 8, but not earlier than at least 60 minutes after end of exercise, the BP will be stopped and the patient will continue with their personal insulin pump.

Clinical Trial Protocol
ZP4207-16051

Version number: 5.0
Amendment 4.0
Date: 02 September 2016

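### With one scheduled on-drug blood pressure reading per visit, the vital-signs component of the primary endpoint is insensitive to transient, asymptomatic falls during dosing

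*Protocol*

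**What the plan says.** Protocol version 6.0, section 7.4.2, lists "Vital signs including body temperature and blood pressure (at visit start and visit end) and weight" among the data collected at Visits 3 and 4. Footnote 9 to the Appendix A schedule agrees: "Vital signs including body temperature and blood pressure will be obtained at visit start and visit end". Section 8.1 names vital signs among the eight components of the primary safety and tolerability endpoint, and section 11.2.1 plans a descriptive summary of them.

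The detailed timing is in section 7.4.1, which is available here only in the version 5.0 text. The first reading is on arrival: "Upon arrival to the visit, the patient's weight and vital signs including body temperature and blood pressure will be documented". The second is at the close: "Just prior to the end of the study visit, vital signs including body temperature and blood pressure will be obtained". The device runs until late in the day: "After approximately Hour 8, but not earlier than at least 60 minutes after end of exercise, the BP will be stopped". To raise glucagon use, the patient's own pump runs at twice its basal rate, and that challenge ends when exercise begins: "At the start of the exercise period, patients will restore their normal basal insulin profile".

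Section 1.5 (also version 5.0 text) states the risk: "Episodes of low blood pressure have also been observed after administration of higher doses of glucagon and ZP4207". Section 7.4.1 lists hypotension among the findings that may prolong observation. In the same visits, nausea, infusion-site pain and Draize scores are taken hourly (section 7.4.2), and a nurse or physician is always present (section 7.4.8).

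**The concern.** The protocol names low blood pressure as an effect seen with both drugs and counts vital signs in its primary endpoint. Between arrival and visit end, however, it schedules no blood pressure reading. A fall that comes and goes within that interval without symptoms has no scheduled route into the data, and no scheduled reading would bring it to the notice of staff deciding on longer observation.

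What is at stake is how an unremarkable result would be read. A table of normal start and end values in both arms could be taken as evidence that ZP4207 and glucagon had no haemodynamic effect during about eight hours of dosing, when it speaks only to the state at the end. No analysis plan can repair this, because readings that were not taken cannot be analysed.

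**Working it through.** The protocol gives no figure on this point to reproduce. The check is a count of readings, a timing calculation and an illustration.

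**1. Scheduled on-drug readings.** There are two readings per visit (section 7.4.2, Appendix A footnote 9), and the first is before dosing (section 7.4.1). That leaves 1 per patient per treatment. With 20 to 24 patients randomized (section 11.2.4), at most 20 to 24 on-drug values on ZP4207 are scheduled in the whole trial, about 10 per part. Hourly readings over about 8 hours would give 20 × 8 = 160 to 24 × 8 = 192.

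**2. How late the one reading falls.** The doubled basal rate stops at the start of exercise, between about Hour 6 and Hour 7. Exercise is 4,000 heart beats at 120–140 per minute:

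- 4,000 / 140 = 28.6 min; 4,000 / 120 = 33.3 min.
- At least 60 min must follow before the device stops: 28.6 + 60 = 88.6 min; 33.3 + 60 = 93.3 min.

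The device therefore stops no earlier than about 89–93 minutes after the doubled rate ends. If exercise starts at Hour 6 and the device stops at Hour 8, the gap is 120 minutes. The end reading is taken close to that time.

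**3. Illustration of sensitivity.** These assumptions are not in the documents: one episode of duration d minutes, uniformly timed over 480 minutes, edge effects ignored. The chance that a scheduled reading falls inside it is d / 480 for one end reading and min(1, d / 60) for hourly readings.

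| d (min) | End reading only | Hourly |
|---|---|---|
| 15 | 15/480 = 3.1% | 25% |
| 30 | 30/480 = 6.25% | 50% |
| 60 | 60/480 = 12.5% | 100% |
| 120 | 120/480 = 25% | 100% |

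If five patients each had an independent 30-minute episode, the chance of catching at least one would be 1 − (1 − 0.0625)^5 = 28% with the end reading and 1 − 0.5^5 = 97% with hourly readings.

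Uniform timing is a convenience. If falls clustered in the doubled-rate period, the end reading would do worse than the table shows; if they clustered after exercise, it would do better.

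**4. A trap in the obvious summary.** With about 8 on-drug readings, the lowest is low partly by chance. For 8 independent normal readings with no drug effect, the expected minimum is about 1.4 within-patient standard deviations below the mean. A change from one start value to the lowest later value would therefore show a fall in both arms even if neither drug did anything.

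**The case against.** The strongest case against is that this is a small feasibility trial with no formal sample size, vital signs are only described, and the documents do not contradict each other. That is correct, and it makes this an improvement to measurement, not the correction of an error.

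Four stronger readings are tempting, and the documents do not support them.

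- **That the endpoint cannot detect a fall in blood pressure.** Adverse events are another component of the same primary endpoint, symptoms are collected during the visit, and staff are always present. A symptomatic fall can be recorded as an adverse event, and a fall that is sustained or present at the close can be seen at the end reading. Only transient, symptom-free falls lack a route.
- **That the gap is peculiar to blood pressure.** The 12-lead ECG, chemistry and hematology follow the same start-and-end schedule in section 7.4.2. What sets blood pressure apart from these is that section 1.5 names a drug effect on it.
- **That exposure will approach a full 1 mg injection within an hour.** Section 6.4 says the device "can administer isolated insulin-glucagon doses once every 5 minutes", and 12 boluses at the 80 microgram cap come to 960 micrograms. That is a ceiling, not a forecast. The same section gives typical doses of 2.5–40 micrograms, an earlier mean of 0.5 mg per day (range 0.2–0.9) and an expected mean below 1.0 mg per day. Section 1.2 adds that the algorithm allows for recent glucagon doses. Section 1.5 ties low blood pressure to higher doses and expects individual doses here to be low. The doubled basal rate is meant to raise glucagon use, so totals may exceed earlier experience, but nothing shown supports an hour near the cap.
- **That the end reading falls after all demand for glucagon has passed.** Section 1.2 gives insulin analog clearance as 4–8 hours, so insulin from the doubled rate may still be acting, and exercise intervenes. The reading is late, but it is not shown to be outside the period of effect.

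The version point also stands: the risk, dose and visit-procedure text is version 5.0, since those sections of version 6.0 are not shown. The reading schedule itself is version 6.0.

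**Conclusion.** The point holds as a cheap improvement. One late on-drug reading per treatment leaves the vital-signs component insensitive to transient, asymptomatic falls in blood pressure during dosing, and normal start and end values would not show their absence. The count of readings and the gap of roughly 90 minutes or more after the challenge ends follow from the protocol's own schedule. The detection figures (about 6% against 50% for a 30-minute fall, 12.5% against 100% for a 60-minute fall) are illustrative and rest on assumed duration and uniform timing. The documents do not say that such falls are likely at the doses expected here.

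**What to change.** In section 7.4.2 and Appendix A footnote 9, add blood pressure and pulse at the existing hourly VAS and Draize assessment at Visits 3 and 4, keeping the visit-start and visit-end readings. Align section 7.4.1 with this.

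Summarize the values by time point and treatment. Compare the lowest on-drug systolic value between ZP4207 and glucagon within patient, separately in Part 1 and Part 2 as section 11 requires; with the same number of readings in both visits, the chance component of the minimum is shared. State that lowest-minus-start within an arm is not to be read as a drug effect.

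The cost is a short amendment, some eCRF rows, about a minute of extra work per hour at a contact that already takes place, and a few incidental low readings to review. No extra visit, blood sample or staff is needed, and dosing and clinical management rules are unchanged.
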